4.2.3 Exploratory Analyses

The exploratory analyses are planned:

- **After Week 12:** to evaluate the change in efficacy from Week 12 to Week 24 in subjects who undergo dose escalation or maintenance at Week 12 in the MITT population who enter the maintenance/escalation period (MITT24),
- **After Week 24:** to explore the effect of withholding M1095 at Week 24 in IGA score of 0 responders in the MITT population who enter the response assessment/dose hold period (MITT48).

Sensitivity analyses for the exploratory analyses after Week 12 and Week 24 will not be performed unless deemed necessary.

4.2.3.1 Exploratory Analyses after Escalation at Week 12

At Week 12, subjects randomized to M1095 30 mg or M1095 60 mg are planned to undergo a dose escalation to M1095 120 mg if they fail to achieve an IGA response i.e. if they have an IGA > 1.

The assessment of change in efficacy from Week 12 to Week 24 will be investigated in the subgroup of subjects who were randomized to 30 mg and 60 mg M1095 at Week 0 and who

underwent dose escalation at Week 12 due to IGA > 1 during the period starting from Week 12 to Week 24 by treatment sequence of the induction and maintenance/escalation periods (the treatment sequence will be the combination of the initial randomized treatment and the administered treatment at Week 12). In addition, the change in longer term efficacy to Week 48 in this subgroup of subjects will be explored.

The exploratory analyses after Week 12 will be conducted in the MITT24 population.

4.2.3.1.1 Variables

The post-Week 12 exploratory objective will be examined with the help of these variables:

Endpoints	Type of Variables	Exploratory Variables
IGA-derived endpoints	Binary	
 proportion of subjects with an IGA response at all visits from Week 12. proportion of subjects with a complete IGA response at all visits from Week 12.
	Categorical	
 shift from Week 12 in IGA score category at all post-Week 12 visits.
	Time-to-Event	
 time to first IGA response from Week 12. time to first complete IGA response from Week 12.
PASI-derived endpoints	Binary	
 proportion of subjects achieving PASI 75/PASI 90/PASI 100 response at all visits from Week 12.
	Continuous	
 raw PASI score at all visits from Week 12. absolute change and percent change from baseline in PASI score at all visits from Week 12. absolute change and percent change from Week 12 in PASI score at all visits from Week 12.

Table 4.6: Exploratory Endpoints and Variables Related to Post-Week 12 Dose Escalation/Maintenance Analyses

The shift from Week 12 in IGA score category at each post-Week 12 visit will be determined from considering the individual IGA score at Week 12 in order to assess:

- worsening/stability in IGA score from baseline,
- improvement in IGA score from baseline.

IGA Score at Week 12	IGA Score at each post-Week 12 Visit				
	0	1	2	3	4
0					
1				Worsening	
2			Stable		
3		Improvement		Response	
4					

The two time-to-event endpoints will measure the planned time interval in weeks between the Week 12 assessment and the first assessment from Week 12 with an IGA response, or a complete IGA response, respectively. Data will be censored at the last assessment visit if the event had not occurred up to that point.

The continuous variables will be imputed with LOCF whereas the categorical variables will be imputed with NRI. No other imputations will be implemented for these exploratory variables unless indicated otherwise.

4.2.3.1.2 Descriptive Analyses

Data will be summarized over time according to the assigned treatment sequence for both induction (Week 0-12) and maintenance/escalation (Week 12-24) periods (refer to Table 4.7) in the subgroup of subjects randomized to M1095 30 and 60 mg at Week 0 who dose escalated:

(2b) 30mg (x4), Q4/Esc to 120mg

(3b) 60mg (x4), Q4/Esc to 120mg.

	Dose Escalation due to IGA > 1 at Week 12?	Treatment Label	
		Maintenance/Escalation Period	Response Assessment/Dose Hold Period
Planned Treatment Group with Dose Escalation		12	24 52
			(in weeks)
(1) - Placebo at Week 0, 1, 2, 3, 4, 6, 8 (and /M1095 120 mg at Week 12, 14, 16 and Q4W)	N/A	Plac/ 120mg (x4), Q4	
(6) - Secukinumab 300 mg at Week 0, 1, 2, 3, 4, 8 (and 12 and Q4W)	N/A	Secukinumab	
(2) - M1095 30 mg at Week 0, 2, 4, 8 (and: (2a) Q4W if no escalation at Week 12)	No	30mg (x4), Q4/ No Esc	
(2b) M1095 120 mg Q4W if escalation at Week 12)	Yes	30mg (x4), Q4/ Esc to 120mg	30mg (x4), Q4/ Esc to 120mg
(3) - M1095 60 mg at Week 0, 2, 4, 8 (and: (3a) Q4W if no escalation at Week 12)	No	60mg (x4), Q4/ No Esc	
(3b) M1095 120 mg Q4W if escalation at Week 12)	Yes	60mg (x4), Q4/ Esc to 120mg	60mg (x4), Q4/ Esc to 120mg
(4) - M1095 120 mg at Week 0, 2, 4, 8 (and 12 and Q8W)	N/A	120mg (x4), Q8	
(5) - M1095 120 mg Q2W at Week 0, 2, 4, 6, 8, 10 (and 12 and Q4W)	N/A	120mg (x6), Q4	

Note: The only treatment groups displayed in all exploratory analyses after Escalation at Week 12 are the treatment groups displayed in bold in the table. The other treatment groups (identified by rows in grey) are only displayed for completeness and information.

Table 4.7: Planned Treatment Groups with Dose Escalation and their Labels for each Treatment Period for Exploratory Analyses after Week 12.

The variables in Table 4.6 will be presented per treatment group for the Maintenance/Escalation Period: at Weeks 12, 14, 16, 20 and 24 and the Response Assessment/Dose Hold Period.

No formal inferential analyses will be conducted. Comparisons of treatment groups (1), (4), (5) and (6) will be presented elsewhere. For treatment groups (2) and (3) after Week 12, comparisons will be biased due to the Week 12 treatment change being based on post-randomization unfavorable event of lack of efficacy. Comparisons after Week 12 based on descriptive statistics will be made between treatment groups of subjects who dose escalated in subjects who were initially randomized to M1095 30 mg and M1095 60 mg at Week 0.

4.2.3.1.3 Binary and Categorical Variables

The number and proportion of subjects for each binary variable of Table 4.6 will be described in a tabulated and graphical manner per treatment group for each visit with the time in weeks since Week 12. The 95 % exact CI of the proportion will also be presented.

Line plots will present the responder proportions (and its 95% CI) by treatment group and over time from Week 12 and possibly, from Week 0.

For the shift analyses, the proportion and number of subjects in each category will be presented by treatment group and over time.

4.2.3.1.4 Continuous Variables

The raw PASI score, absolute and percent change from baseline will be described for all visits in the same tabular and graphical way as in Section 4.2.2.2.3 per treatment group.

Means of absolute change from baseline in PASI and their associated standard error will be displayed graphically over time by treatment group.

These descriptive statistics above will also be produced for change and percent change from Week 12 in PASI.

A mean/SE plot of improvement in PASI over time will also be created, showing the effect of dose escalation from Week 12.

4.2.3.1.5 Time-to-event Variables

Time-to-event variables will be graphically presented by treatment group using Kaplan-Meier curves. The number of subjects that are still at risk (Pocock et al, 2012) will also be displayed under the time axis. In addition, the following descriptive statistics will be presented by treatment group:

- The number and percentage of IGA response, complete IGA response and censored data at each visit,
- The median time (or other percentile) to IGA response or complete IGA response along with its 95% confidence interval.

4.2.3.1.6 Subset Analyses

The exploratory post-Week 12 analyses will be repeated to assess the longer-term efficacy in the MITT48 population that includes the MITT subjects who completed the maintenance/escalation period and who entered the dose assessment/dose hold period.

Given the study design that allows subjects to dose escalate to the highest dose of M1095 at Week 12 following post-randomization efficacy assessments, selected exploratory analyses may be performed in a subset of subjects with similar post-baseline efficacy characteristics. The purpose of this population is to investigate the differences in a descriptive manner between subjects with similar post-baseline efficacy characteristics at the start of the considered period who had a dose change and those who did not have a dose change. Therefore, an additional population may be derived for this purpose:

Population	Description
Week 12 IGA Non-Responder Population	
Week 12 IGA non-Responder Population is a subset of MITT12 population. This population includes all MITT12 subjects who are classified as IGA non-responders at Week 12 (i.e. with IGA > 1).
 
Subjects will be analyzed according to planned treatment in the maintenance/escalation period (from Week 12 to Week 24).

Table 4.8: Definition of Additional Analysis Population for Exploratory Analyses

The exploratory post-Week 12 analyses may be repeated in the Week 12 IGA non-Responder Population. The aim is to compare all treatment groups from Week 12 to Week 24 in the MITT subjects who enter the maintenance/escalation period but who had an unfavorable efficacy event at Week 12 (all treatment groups will be included except for (2a) and (3a) – refer to Table 4.7).

4.2.3.2 Exploratory Analyses after Withholding/Restarting M1095 from Week 24

From Week 24, subjects receiving M1095 who were not escalated from M1095 30 mg or M1095 60 mg at Week 12 will have their M1095 treatment withheld (placebo will be given) if their IGA score equals 0 at Week 24. If their IGA score is 1 or more at Week 24, these subjects will stay on current dose.

Then, withheld subjects will restart M1095 at the previous dose level (Q4W) at the first visit post-Week 24 when their IGA is 1 or more.

The exploratory analyses after Week 24 will be conducted in the MITT48.

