For purposes of analysis, the following populations are defined:

Population	Description
Enrolled	All subjects who sign informed consent.
Intent-to-Treat (ITT)	
The Intent-to-Treat (ITT) population includes all subjects randomly allocated to a treatment.
 
Subjects will be analyzed according to planned treatment in the induction period (up to Week 12).

Modified Intent-To-Treat (MITT) including MITT12, MITT24 and MITT48	
The Modified Intent-to-Treat up to Week 12 (MITT12) population includes all subjects in the ITT population who receive at least one injection, have a baseline, and at least one post-baseline efficacy assessments up to Week 12.
 
Two additional MITT populations will be defined for exploratory analyses after Week 12 and after Week 24:
 
 • MITT24 that includes all MITT12 subjects who received at least one injection during the escalation/maintenance period from Week 12 to Week 24, • MITT48 that includes all MITT12 subjects who received at least one injection during the response assessment/dose hold period from Week 24 to Week 48. 
Subjects will be analyzed according to planned treatment:
 
 • in the induction period (up to Week 12) for MITT12, • in the maintenance/escalation period (from Week 12 to Week 24) for MITT24, • in the response assessment/response hold period (from Week 24 to Week 48) for MITT48.
Per-Protocol (PP) including PP12, PP24 and PP48	
The Per-Protocol (PP) population includes all subjects in the MITT population who have no important clinical protocol deviations affecting the assessment of efficacy.
 
Three PP populations will be defined:
 
 • PP12 population: PP population up to Week 12 including subjects in the MITT12 population • PP24 population: PP population up to Week 24 including subjects in the MITT24 population • PP48 population: PP population up to Week 48 including subjects in the MITT48 population.

Population	Description

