Binary	Exploratory (escalation): IGA score of 0 or 1, IGA score of 0, PASI responses	12-24	MITT24 & subjects who escalated due to IGA > 1	NRI		●	●
			Week 12 IGA non-responder	NRI			(●)
	12-52	MITT48 & subjects who escalated due to IGA > 1	NRI			●	
	Exploratory (dose hold): IGA score of 0 or 1, IGA score of 0, PASI responses during the M1095 dose hold interval, PASI responses after M1095 restart	24-52	MITT48 & subjects who are eligible to dose hold	None (CC)		●	●
Categorical	Secondary: Shift from baseline in IGA score category	0-12	ITT	LOCF	●		●
		12-24	ITT	LOCF		●	●
		24-52	ITT	LOCF			●
	Exploratory (escalation): Shift from Week 12 in IGA score category	12-24	MITT24 & subjects who escalated due to IGA > 1	LOCF		●	●
			Week 12 IGA non-responder	LOCF			(●)
	12-52	MITT48 & subjects who escalated due to IGA > 1	LOCF			●	
Exploratory (dose hold): Shift from Week 24 in IGA score category	24-52	MITT48 & subjects who are eligible to dose hold	None (CC)			●	
Time-to-event	Secondary: Time to first IGA/complete IGA response from baseline	0-52	ITT	None		● ⁺	●
	Exploratory (escalation): Time to first IGA/complete IGA response from Week 12	12-52	MITT24 & subjects who escalated due to IGA > 1	None		● ⁺	●
	Exploratory (dose hold): Time to first IGA ≥ 1 from Week 24, time to first complete IGA response from M1095 restart	24-52	MITT48 & subjects who are eligible to dose hold	None		● ⁺	●

Type of Variables	Variables	Period (Week – Week)	Analysis Population	Imputation (See Section 4.1.1)	IA1	IA2*	Final
Continuous	Secondary: change and percent change from baseline in PASI	0-12	ITT	LOCF	●		●
				None (CC)			(●)
				MI			(●)
		12-24	ITT	LOCF		●	●
				None (CC)			(●)
		24-52	ITT	LOCF			●
	None (CC)				● ⁺	(●)	
	Secondary: Absolute change from baseline in percentage of total BSA affected by plaque-type psoriasis	0-12	ITT	LOCF		●	●
				None (CC)			(●)
		12-24	ITT	LOCF		●	●
				None (CC)			(●)
		24-52	ITT	LOCF			●
				None (CC)		● ⁺	(●)
	Exploratory: change from baseline in DLQI, SF-36, EQ-PSO	0-12	ITT	LOCF		●	●
		12-24	ITT	LOCF		●	●
		24-48	ITT	LOCF			●
	Exploratory (escalation): change and percent change from baseline/Week 12 in PASI	12-24	MITT24 & subjects who escalated due to IGA > 1	LOCF		●	●
				Week 12 IGA non-responder			(●)
		24-52	MITT24 & subjects who escalated due to IGA > 1	LOCF		● ⁺	●
				Week 12 IGA non-responder			(●)
12-52		MITT48 & subjects who escalated due to IGA > 1	LOCF			●	
			None (CC)		● ⁺	●	

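### Table 4.4 gives response rates after Week 24 in escalated subjects only in MITT48, so those who leave before any Week 24–48 injection are never scored as non-responders

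*SAP*

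**What the plan says.** SAP Section 3 defines two populations for the exploratory work: "MITT24 that includes all MITT12 subjects who received at least one injection during the escalation/maintenance period from Week 12 to Week 24", and "MITT48 that includes all MITT12 subjects who received at least one injection during the response assessment/dose hold period from Week 24 to Week 48". Section 4.2.3.1.6 describes the second as one that "includes the MITT subjects who completed the maintenance/escalation period and who entered the dose assessment/dose hold period".

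Section 4.2.3.1 sets the aim of describing change from Week 12 to Week 24 in subjects escalated from 30 mg or 60 mg, adds an exploration to Week 48 in the same subjects, and closes: "The exploratory analyses after Week 12 will be conducted in the MITT24 population". Section 4.2.3.1.2 presents the Table 4.6 variables for both the maintenance/escalation and the response assessment/dose hold periods. Section 4.2.3.1.6, a section on subset analyses, then adds: "The exploratory post-Week 12 analyses will be repeated to assess the longer-term efficacy in the MITT48 population".

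Table 4.4 assigns the binary escalation endpoints as follows:

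- Weeks 12–24: "MITT24 & subjects who escalated due to IGA > 1", NRI, at the second interim and final analyses.
- Weeks 12–52: "MITT48 & subjects who escalated due to IGA > 1", NRI, at the final analysis.

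No other row covers binary response in escalated subjects after Week 24. The optional Week 12 IGA non-responder row stops at Week 24 for these endpoints. Section 4.1.1.2 defines NRI so that a missed assessment, or stopping treatment or study for any reason, counts as non-response.

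**The concern.** NRI can act only on subjects inside the analysis population. An escalated subject who stops before any Week 24–48 injection is outside MITT48. In the Week 12–52 table that subject leaves the denominator and is never imputed as a failure.

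The loss may well be related to outcome. Only subjects with IGA above 1 at Week 12 escalate. SAP Section 4.1.1 names lack of efficacy among the reasons for stopping treatment, and Protocol Section 6.6.2 asks the investigator at Week 24, the point of entry to MITT48, to consider discontinuing subjects whose psoriasis has worsened from baseline. What is at stake is how the descriptive rates after Week 24 read: as written they describe escalated subjects who stayed, while a reader could take them as rates among all who were escalated.

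**Working it through.** **The rows side by side.** Population used in Table 4.4 for escalated subjects, leaving out the optional Week 12 IGA non-responder rows:

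| Endpoint | Visits to Week 24 | Visits after Week 24 |
|---|---|---|
| IGA 0/1, IGA 0, PASI 75/90/100 (NRI) | MITT24, and MITT48 within the 12–52 row | MITT48 only |
| Time to first IGA or complete IGA response | MITT24 | MITT24 |
| PASI change and percent change (LOCF) | MITT24, and MITT48 within the 12–52 row | MITT24 (24–52 row) and MITT48 |
| Shift in IGA (LOCF) | MITT24, and MITT48 within the 12–52 row | MITT48 only |

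The time-to-event and PASI change rows show that the SAP already carries MITT24 past Week 24 in escalated subjects. The binary endpoints, where NRI would do its work, do not get this.

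**Effect on the rate.** Let N be the escalated subjects in MITT24, d those among them with no Week 24–48 injection, and r the responders at a visit after Week 24. Under NRI none of the d subjects can be a responder at such a visit, so:

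- MITT24 rate = r/N
- MITT48 rate = r/(N − d)
- Ratio = 1/(1 − d/N), which is never below 1

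| d/N (assumed) | 5% | 10% | 15% | 20% | 30% |
|---|---|---|---|---|---|
| Multiplier | 1.05 | 1.11 | 1.18 | 1.25 | 1.43 |

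The fixed direction holds only for visits after Week 24. At earlier visits a subject who later leaves may still have been a responder, so the two tables can differ either way.

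**How many subjects.** The documents give no figure for this analysis: no number escalated, no early exit rate and no response rate after escalation. The one planning input that bears on it is the assumed IGA 0/1 rate above 88% on drug (SAP Section 5). With 50 per arm, 50 × (1 − 0.88) = 6, so about 6 or fewer per arm would escalate. If Week 12 response were 80% (assumed), 50 × 0.20 = 10 per arm would.

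Section 4.2.3.1.2 reports the 30 mg and 60 mg escalators separately, so the examples are per arm, with r and d assumed:

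| N | d | r | MITT24 with NRI | MITT48 with NRI |
|---|---|---|---|---|
| 6 | 0 | 3 | 3/6 = 50.0% | 3/6 = 50.0% |
| 6 | 1 | 3 | 3/6 = 50.0% | 3/5 = 60.0% |
| 6 | 1 | 4 | 4/6 = 66.7% | 4/5 = 80.0% |
| 10 | 1 | 5 | 5/10 = 50.0% | 5/9 = 55.6% |
| 10 | 2 | 5 | 5/10 = 50.0% | 5/8 = 62.5% |

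**The case against.** The strongest reply is that the text already makes MITT24 the base. Section 4.2.3.1 names it directly after the Week 48 aim, Section 4.2.3.1.2 carries the variables into the dose hold period, and Section 4.2.3.1.6 only repeats the analyses in MITT48. That is a fair reading, and it narrows the point to a mismatch between text and table. It does not remove it, because Table 4.4 is where populations and imputation are assigned, and it has no MITT24 binary row after Week 24.

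A reader might infer that every longer-term escalation result drops early leavers, or that NRI is switched off. The documents do not support either. Time to response (Weeks 12–52) and PASI change (Weeks 24–52) keep MITT24. NRI still applies within MITT48 to subjects who leave after entering it. Early leavers count as failures in the Week 12–24 MITT24 table, which serves the stated exploratory objective.

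A reader might also infer that a trial conclusion about escalating is biased. Section 4.2.3.1.2 plans no formal inference here and warns that comparisons for these arms after Week 12 are biased. Section 4.2.2 analyses longer-term response by randomized arm in ITT whatever the escalation status. Section 4.6.1 tabulates completion and reasons for stopping in MITT24 and MITT48, so the exclusion can be traced.

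Finally, the numbers are small. Pooling both arms, which no planned table does, 6/12 has an exact 95% interval of about 21–79% and 6/10 about 26–88%. The shift lies well inside the sampling error. That stands, but it does not justify a denominator that can move the rate in one direction only. That leavers are mostly treatment failures is plausible but not shown: Section 4.1.1 also lists adverse events and noncompliance.

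**Conclusion.** The point holds as a minor one. If Table 4.4 is followed as written, the only binary response rates after Week 24 in escalated subjects are conditional on having received an injection in Weeks 24–48, and they equal or exceed the MITT24 NRI rates by the factor 1/(1 − d/N). That is 1.11 to 1.25 if 10–20% leave early, which is an assumption since the documents give no exit rate. With no early leavers there is no difference. The direction after Week 24 follows from NRI alone and does not depend on why subjects leave.

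The affected results are descriptive. No test, power figure or primary conclusion changes, and the secondary ITT analyses and the Week 12–24 MITT24 results stand as planned.

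**What to change.** In Table 4.4, add a row for the binary escalation endpoints in MITT24 and escalated subjects, with NRI through Week 52, and mark it as the main analysis. Keep the MITT48 row as supportive, labelled as conditional on entering Weeks 24–48, and footnote the number escalated but not in MITT48, with reasons. Align Sections 4.2.3.1 and 4.2.3.1.6 so that both name MITT24 as the base to Week 52 and MITT48 as the repeat. The IGA shift row has the same gap after Week 24 and could be aligned in the same edit.

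The cost is a few SAP rows, two short text edits and one more set of descriptive tables. No new data are needed.

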4.2.3.2.1 Variables

The post-Week 24 exploratory objectives will be explored with these variables:

Endpoints	Type of Variables	Exploratory Variables
IGA-derived endpoints	Binary	
 proportion of subjects with an IGA response at all visits from Week 24. proportion of subjects with a complete IGA response at all visits from Week 24. proportion of subjects requiring M1095 restart after withholding study drug at each visit from Week 24. cumulative proportion of subjects with M1095 restarted after withholding study drug at each visit from Week 24.
	Categorical	
 shift from Week 24 in IGA score category at all post-Week 24 visits.
	Time-to-Event	
 time to first IGA ≥ 1. time from M1095 restart to first complete IGA response during Week 24-48 interval.
PASI-derived endpoints	Binary	
 proportion of subjects achieving PASI 75/PASI 90/PASI 100 response at all visits from Week 24. proportion of subjects achieving PASI 75/PASI 90/PASI 100 response by visit during the M1095 dose hold interval. proportion of subjects achieving PASI 75/PASI 90/PASI 100 response at all visits after M1095 restart.
	Continuous	
 raw PASI score at all visits from Week 24. absolute change and percent change from baseline in PASI score at all visits from Week 24. absolute change and percent change from Week 24 in PASI score at all visits from Week 24. raw PASI score by visit during the M1095 dose hold interval. raw PASI score at all visits after M1095 restart. raw PASI score after M1095 restart as a function of time in weeks.

Table 4.9: Exploratory Endpoints and Variables Related to Post-Week 24 Dose Hold/Restart Analyses

Missing continuous or categorical variables will not be imputed. Time-to event data will be censored at the last assessment visit if the event had not occurred up to that point.

